11.2 Secondary outcome(s)

The secondary outcome is to determine if following assessment with MAPLe targeted treatment is achieved. This will be defined by improvement in physiological assessment with MAPLe and incontinence questionnaires. This will be measured at 6 months following the end of recruitment at the end of study.

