Main inclusion/exclusion criteria:	Inclusion: Symptoms of FI, aged over and including 18, capacity to consent, male/female. Exclusion: anal cancer, anal surgery in the last 3 months, acute/painful perianal disease.
Statistical methodology and analysis:	Non-inferiority testing of MAPLe in the assessment of FI will be performed using Bland Altman method. MAPLe will be tested against HRAM and AUS.
	Participants will be grouped according their pathology: Fistula/chronic perianal disease, Obstetric injury <12 months, Obstetric injury >12 months, neuropathic sphincter. Correlation studies and regression analysis to identify which groups benefitted from MAPLe assessment.
	The clinical utilisation of MAPLe will be determined by the outcome of an expert panel.
	Comparative analysis of participant pre and post treatment MAPLe results will identify if targeted treatment has been achieved.

3. Background and Rationale

Burdon of Disease

Faecal incontinence (FI) is defined as the involuntary passage of gas, liquid or solid stool. The symptom is experienced by an estimated 1-10% of the population. FI is associated with a multitude of disease pathologies and prevalent in vulnerable patient groups, the elderly, learning disabilities or severe co-morbidities, and most prevalent in multiparous females. The degree of symptomatic severity is varied and can result in psychological destress and social withdrawal, severely impacting quality of life in up to 22% of suffers(1).

There is significant economic burden associated with FI. Health economic studies have identified US\$4110 as an average annual cost per person, with an increased cost associated with increased symptom severity(2). Further studies estimated a US \$11 billion annual expenditure and a 55% increase in personal cost of health for sufferers(3). Treatment is symptom orientated, further research would improve understanding of the symptom and direct treatment for more effective outcomes.

Anatomy and Physiology of the Pelvic Floor

FI is the result of impairment to the structure or function of the pelvic floor(4). The pelvic floor, levator ani, is a sheet of muscle supporting the weight of the abdominal cavity. It is divided into four muscle groups: pubococcygeus, ilio-coccygeus, coccyges and puborectalis, assisting the maintenance of faecal and urinary continence.

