3.1 Assessment and Management of Risk

The table below summarise the risks and mitigations of all test above standard care that are being performed in a table:

Intervention	Potential risk	Risk Management
Assessment with MAPLe device	The device will be placed anally and record sEMG, not providing stimulation. As the device will be used in the same nature as current assessment devices no additional risk is perceived.	Performed by trained operator.

4. Objectives

Primary: To determine the role of MAPLe in the assessment of FI in defined patient groups.

Secondary: To determine if targeted treatment is achieved following assessment with MAPLe.

5. Trial design

This is cohort study of participants with symptoms of faecal incontinence. It will take place across two hospital trusts, both able to provide specialist pelvic floor services and facilities required to meet the needs of the study and follow up required by the participants. The use of two sites aims to increase the yield and diversity of participants. The sample size for the study is 120 participants.

Following a stringent selection and recruitment process, participants will be invited to a designated ARP session where they will be consented, complete an incontinence and quality of life questionnaire, and undergo ARP assessment. This will comprise of the current gold standard, AUS and HRAM, and additional assessment with MAPLe using a standardised protocol. Through undertaking all three tests participants will act at their own controls. Participant participation will conclude following ARP assessment unless treatment is deemed necessary by their local MDT. These participants will be followed up at 6 months with interval MAPLe assessment and incontinence and quality of life questionnaire.

The results will undergo statistical analysis to determine non-inferiority of MAPLe in assessing FI. For analysis participants will be allocated to the following groups: fistula/chronic perianal conditions, obstetric injury <12 months, obstetric injury >12months, neurogenic. Each group will be analysed using symptoms profile and MAPLe results to identify correlation. Comparison of MAPle results pre and post treatment will determine if targeted treatment has been achieved.

An expert panel of pelvic floor specialists will be formed to determine the additional benefit of MAPLe in a clinical context. The panel will consist of 3-6 specialists within the field. To reduce bias,

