8.4 Subsequent assessments and procedures

The ARP results for each participant will be discussed at their local multi disciplinary team meeting in accordance with current practice. Participants who are offered treatment will be followed up at 6 months in their recruiting trust for repeat assessment with MAPLe. Participants who are offered neuromodulation will receive interval assessment with MAPLe during the placement of the implanted device. Should not follow up be offered participation is complete.

A schedule of all trial assessments and procedures is set-out in Appendix 1.

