11.5.2 Secondary outcome analysis

To determine if targeted treatment has been achieved participants will be grouped according to the treatment received: biofeedback, neuromodulation, rectal irrigation, and surgery.

Statistical comparison between MAPLe results pre and post treatment for each participant per group will be performed and analysed.

12. Record keeping and archiving

At the end of the trial, all essential documentation will be archived securely by the CI for a minimum of 20 years from the declaration of end of trial.

Essential documents are those which enable both the conduct of the trial and the quality of the data produced to be evaluated and show whether the site complied with all applicable regulatory requirements.

The sponsor will notify sites when trial documentation can be archived. All archived documents must continue to be available for inspection by appropriate authorities upon request.

13. Oversight Committees

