Appendix 1 - Schedule of assessments

	Screening (Pre- treatment assessment)	Intervention phase		Final visit	
Visit No:	1	2	3	4	
	Day – X to Day -X	Day 1	Day 7	6 Months	
Window of flexibility for timing of visits:			+/- 7 Days	+/- 14 days	
Informed Consent		Х			
Medical History	Х				
Physical Examination					
Eligibility confirmation	Х	Х			
Faecal incontinence Questionnaire		Х			
Quality of Life Questionnaire	Х				
Anal Ultrasound	UCLH X	ASPH X			
Prescribed History		Х			
HRAM		Х			
MAPLe		Х		If treatment advised x	
MDT			Х		
Adverse Events review	Х	Х	Х	Х	
Concomitant Medication review (if applicable)	Х	Х			

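### The secondary outcome rests on MAPLe and incontinence questionnaires, but the planned pre/post analysis uses MAPLe alone and the visit schedule omits the questionnaires at 6 months

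*Combined protocol and SAP*

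**What the plan says.** Section 11.2 gives the secondary outcome two components: "This will be defined by improvement in physiological assessment with MAPLe and incontinence questionnaires".

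The analysis of that outcome is described in three places:

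- Section 11.5.2 groups participants by treatment received (biofeedback, neuromodulation, rectal irrigation, surgery) and then states: "Statistical comparison between MAPLe results pre and post treatment for each participant per group will be performed and analysed".
- Section 5 (Trial design): "Comparison of MAPle results pre and post treatment will determine if targeted treatment has been achieved".
- Section 2 (Summary): "Comparative analysis of participant pre and post treatment MAPLe results will identify if targeted treatment has been achieved".

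The 6-month visit is also described in three places:

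- Section 5: "These participants will be followed up at 6 months with interval MAPLe assessment and incontinence and quality of life questionnaire".
- Section 8.4: "Participants who are offered treatment will be followed up at 6 months in their recruiting trust for repeat assessment with MAPLe". It then refers the reader onward: "A schedule of all trial assessments and procedures is set-out in Appendix 1".
- Appendix 1 marks a conditional MAPLe and an adverse events review at 6 months. The row "Faecal incontinence Questionnaire" has a single mark, at Visit 2 (Day 1). The quality of life row has a single mark, at Visit 1.

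**The concern.** An outcome, its data collection and its analysis should describe the same thing. Here the definition asks for improvement in physiology and in symptoms, the analysis covers physiology only, and the operational sections disagree on whether symptoms are measured after treatment at all.

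The protocol's own background shows why this matters. Section 3 says that progression through treatments is guided by response as measured on FI scores. It also cites a study of 218 patients in which anorectal physiology did not correlate with FI scores, and says repeat physiology is not done after treatment because studies showed no improvement. Those statements concern existing tests, not surface EMG. But Section 3 also lists the link between MAPLe and symptoms, and the change in MAPLe after treatment, among the questions this study is meant to answer. A change in MAPLe therefore cannot be assumed to stand in for a change in symptoms.

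As written, the trial would either declare targeted treatment achieved on one component or be unable to report the outcome as 11.2 defines it. A missed score is also hard to recover: the St Mark's categories in Appendix 3 refer to the preceding 4 weeks, so a 6-month score cannot be reliably rebuilt later.

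**Working it through.** The plan gives no figure to reproduce. The check sets the passages side by side.

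**Step 1: does any pre/post analysis use a questionnaire?**

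| Place | MAPLe | Questionnaire |
|---|---|---|
| Section 2, Summary | yes | no |
| Section 5 | yes | no |
| Section 11.5.2 | yes | no |

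Count with a questionnaire: 0 of 3. The correlation of symptom profile with MAPLe in Sections 11.1 and 11.5.1 belongs to the primary outcome and is not a before-and-after comparison, so it does not fill the gap. Components of the 11.2 definition with a planned analysis: 1 of 2.

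**Step 2: is the questionnaire collected at 6 months?**

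| Place | MAPLe | Incontinence questionnaire | Quality of life questionnaire |
|---|---|---|---|
| Section 5 | yes | yes | yes |
| Section 8.4 | yes | not named | not named |
| Appendix 1, 6-month column | if treatment advised | no mark | no mark |

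Count with a questionnaire: 1 of 3. Section 10.2 adds a sentence placing all required data collection at the anorectal physiology session. Taken literally, that leaves no room for any 6-month measurement, MAPLe included.

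**Step 3: could the blank cells be lost in text extraction?** Unlikely. In the same table the adverse events row keeps a mark in all four visit columns and the MAPLe row keeps its 6-month entry, while each questionnaire row has exactly one mark.

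**Step 4: what follows under each reading?**

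- Section 8.4 and Appendix 1 followed: there is no post-treatment symptom score, and the questionnaire component cannot be evaluated. The MAPLe component still can.
- Section 5 followed: the scores exist, but no analysis is specified for them.

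Neither reading delivers the outcome as 11.2 defines it.

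**Step 5: how many participants?** Only those offered treatment. The documents give no rate, so the following rates are assumptions applied to the planned 120:

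- 25%: 120 × 0.25 = 30
- 50%: 120 × 0.50 = 60
- 75%: 120 × 0.75 = 90

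**Separate observation.** Appendix 1 marks the quality of life questionnaire at Visit 1 and informed consent at Visit 2. Section 6.4 rules out trial procedures before consent, and Sections 5 and 8.3 place the questionnaire at the physiology session. This is a scheduling conflict and has no bearing on 11.2, which names only incontinence questionnaires.

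**The case against.** The best defence is that this is loose drafting. The Summary and Section 5 may simply abbreviate 11.5.2, in which case there is one analysis with one omission, not three. Section 5 plainly intends the 6-month questionnaires. Appendix 1 is incomplete even for MAPLe: Section 8.4 plans an interval MAPLe during neuromodulation device placement that the schedule does not show. Its silence on questionnaires therefore looks like oversight. Section 8.3 has the student researcher carry out the assessments, which makes divergence between sites less likely. One could also restore consistency by cutting 11.2 back to MAPLe.

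Much of this is fair as an account of how the mismatch arose, but it does not remove it. Even with one analysis and full collection, 11.5.2 gives the questionnaire no role, and leaving that role to be settled after the data are seen invites selective reporting. An incomplete schedule is a reason to correct it, especially as Section 8.4 presents it as the full list. Narrowing 11.2 is a legitimate alternative, but it would leave the claim of targeted treatment with no symptom evidence, for which the protocol's background gives little support.

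One further point stands. Section 11.2 sets no threshold for improvement and does not say outright that both components must improve, although its conjunction can be read that way. Reporting both changes supplies the evidence; the decision rule still has to be written down.

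**Conclusion.** The concern holds and should be fixed. One of the two components of the secondary outcome has no planned analysis, and two of the three descriptions of the 6-month visit omit its measurement. The conclusion rests on the current text alone and on no statistical assumption; only the 30, 60 and 90 figures depend on assumed treatment rates. The effect is confined to the questionnaire component of the secondary outcome in participants offered treatment. The MAPLe component and the primary outcome are not affected.

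**What to change.** 1. In Appendix 1, mark the incontinence and quality of life questionnaires at Visit 4 for participants offered treatment.
2. Bring Section 8.4 into line with Section 5, and reword the sentence in Section 10.2 so that it allows for 6-month data.
3. In 11.5.2, add the within-participant pre/post change in St Mark's score for each of the four treatment groups already listed, reported alongside the MAPLe change.
4. Word the Summary and Section 5 to match 11.2.
5. In the same edit, state in 11.2 what counts as improvement on each component and whether both are required. Give the 6-month quality of life data a stated use, so that they are not collected without a purpose.
6. Separately, move the baseline quality of life mark in Appendix 1 from Visit 1 to Visit 2, after consent.

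The cost is a few schedule marks and short wording changes, plus a few minutes of questionnaire time per treated participant. No extra visits, staff or participants are needed.

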The NHS spends an estimated £100 million on treatment for FI and it is thought patients experience symptoms for 5 years before seeking treatment. If community management of dietary advice, simple anti-diarrhoeal medication and good toileting (17) fail patients are referred to secondary care. Choice of treatment can vary between trusts due to resources and expertise. The treatment options for FI include: medications, biofeedback, rectal irrigation, neuromodulation and other surgical interventions. Patients are referred in a stepwise progressive pattern. This directed by their response to treatment, quantified by FI scores.

Biofeedback is the process of electronically monitoring an autonomic function to acquire voluntary control. Biofeedback treatment for FI has three elements: rectal sensitivity training to improve awareness and response to stool in the rectum, strength training of the pelvic floor using manometric or electromyographic stimulus, or co-ordination training. Biofeedback treatment protocols are varied(18), however 70-80% experience a 50% improvement of symptoms (19). More recent studies have found no significant improvement in symptoms following treatment with biofeedback(20) and biofeedback has been shown to have the same symptom improvement as dietary advice and routine pelvic floor exercises(21).

Rectal irrigation is a treatment for both constipation and FI. The treatment aim is to maintain an empty rectum(22) preventing incontinence episodes(23). Irrigation is performed using a catheter placed in the rectum through which fluid is irrigated resulting in evacuation of the rectum. The treatment has been found to improve symptoms by 44%.

Short title: Assessment of FI with MAPLe

Sponsor code: 119731

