Studies performed at other centers have investigated the use of surface electrodes (sEMG) on probes(34) placed anally to identify abnormalities or abnormal variants in the innervation and propagation of stimulus within the EAS(35). The anal probes have a series of circumferential sensors that identify the origin and direction of propagation of an action potential. The origin correlates to the

location of an NMJ and innervation zone(19). This technique has been used to investigate asymmetric innervation of the anal canal, particularly important in obstetric medicine(36), but has not progressed from research into clinical utilisation.

The MAPLe device is a new medically certified device distributed by Novuqare using the principals of sEMG in the diagnosis and management of pelvic floor complaints (figure 1).

Figure 1 MAPLe device: anal probe, sEMG detector and charging station.

The probe l has 24 surface electrodes positioned in circumferential bands along its length (figure 2), it is placed in the anal canal. Each sensor detects the sEMG activity in mV for the most proximal muscle fibers (figure 3).

Figure 3 MRI of pelvis with anal probe in situ, confirming correct placement for sEMG detection.

The results are analysed by the receiver to provide numerical values. The values are displayed as a target shaped diagram depicting locational functionality (figure 4 & 5), giving a clear representation of precise areas of weakness in the pelvic floor.

Figure 4 The results can be displayed in three views.

Figure 5 Sensors are grouped together according to the muscle they represent.

The results are displayed on a hand held device in both numerical and diagrammatic formats (figure 6).

Figure 6 Results are displayed on screen in greyscale on target or numerical value.

An independent study tested MAPLe on 229 asymptomatic healthy participants. The study confirmed accurate probe placement to ensure sEMG correlated with correct muscular group, and identified a normal range (27). MAPLe is currently used to provide biofeedback for patients with FI by identifying and targeting muscles with reduced sEMG via visual and electrical stimulation.

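### Improvement from before to after treatment, with no comparator, is taken as proof that treatment was targeted, and nothing in the measure concerns targeting

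*Combined protocol and SAP*

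**What the plan says.** Section 11.2 sets the question: "The secondary outcome is to determine if following assessment with MAPLe targeted treatment is achieved". It then gives the criterion: "This will be defined by improvement in physiological assessment with MAPLe and incontinence questionnaires". No size of change is specified.

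Three other places use MAPLe alone:

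- Section 5 (Trial design): "Comparison of MAPle results pre and post treatment will determine if targeted treatment has been achieved".
- Section 2 (Summary, statistical methodology): "Comparative analysis of participant pre and post treatment MAPLe results will identify if targeted treatment has been achieved".
- Section 11.5.2: "Statistical comparison between MAPLe results pre and post treatment for each participant per group will be performed and analysed". The groups are formed after the event: "participants will be grouped according to the treatment received: biofeedback, neuromodulation, rectal irrigation, and surgery".

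Under section 5, section 8.4 and the schedule in Appendix 1, repeat MAPLe at 6 months is only for participants offered treatment. The others finish after the baseline assessment. The remark in section 5 that participants are their own controls refers to having all three tests (AUS, HRAM and MAPLe) at baseline, not to the effect of treatment.

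On the device, the Rationale in section 3 notes: "MAPLe is currently used to provide biofeedback for patients with FI".

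**The concern.** The outcome is named for one thing and measures another. Targeting is a statement about how treatment was chosen or where it was directed. The criterion is a statement about whether values moved. A participant whose treatment had nothing to do with the MAPLe result counts as a success if the values improve. A participant whose treatment was aimed exactly at the weak area MAPLe showed counts as a failure if they do not.

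Without a comparator, the change also cannot be attributed to anything in particular. It could come from any effective treatment, non-specific improvement, regression to the mean, or practice on the device where MAPLe was also the biofeedback tool. At stake is the study's only secondary conclusion: a positive result would be reported as evidence that MAPLe leads to targeted treatment, which the analysis cannot show.

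**Working it through.** **1. The logical step.** Set the question in 11.2 (was treatment targeted?) beside the criterion (did MAPLe and questionnaires improve?) and the analysis in 11.5.2 (pre against post MAPLe, by treatment received). No variable in either section links the treatment to a MAPLe finding. This gap needs no arithmetic.

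**2. The protocol's own background.** The Treatment part of section 3 cites 70–80% of biofeedback patients gaining a 50% improvement in symptoms, and biofeedback doing no better on symptoms than dietary advice and routine exercises. On those figures, treatment chosen without this study's MAPLe assessment can meet the questionnaire part of the criterion.

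**3. What can be reproduced.** Section 11.3 gives 4 × 30 = 120, which is right as arithmetic. The 30 is per diagnostic group. The secondary analysis uses four treatment groups among treated participants only, so their sizes are unknown. No alpha, SD, repeatability or treated fraction is stated. Everything below rests on assumed inputs.

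**4. Regression to the mean with zero treatment effect.** Take baseline and 6-month MAPLe as bivariate normal with SD 1 and test-retest reliability ρ. If the lowest fraction f at baseline is treated, the mean baseline deficit is λ = φ(z_f)/f, and the expected spurious gain is (1 − ρ)λ.

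- f = 0.25: λ = 1.27, gain 0.25 SD (ρ = 0.8) to 0.51 SD (ρ = 0.6).
- f = 0.50: λ = 0.80, gain 0.16 to 0.32 SD.
- f = 0.75: λ = 0.42, gain 0.08 to 0.17 SD.

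If selection is on another variable correlated c with baseline MAPLe, the gain becomes c(1 − ρ)λ. With c = 0.3 and half treated, this is 0.3 × 0.2 × 0.80 = 0.05 SD to 0.3 × 0.4 × 0.80 = 0.10 SD.

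Simulated chance of a significant gain on a paired t-test (two-sided 0.05, so nominally 2.5% in the direction of improvement), n = 30, ρ from 0.8 to 0.6:

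| Who is treated (assumed) | Significant gain with no effect |
|---|---|
| Selection unrelated to baseline MAPLe | about 2.5% |
| Half, on a variable correlated 0.3 with MAPLe | 6–9% |
| Lowest three-quarters on MAPLe | 10–18% |
| Lowest half on MAPLe | 28–53% |
| Lowest quarter on MAPLe | 59–91% |

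Wherever selection is related to MAPLe, rates are lower at n = 15: for the lowest three-quarters they fall to about 7–11%.

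**5. A non-specific shift from any cause.** With pre/post correlation r, the SD of the change is √(2(1 − r)). For n = 30, a shift of 0.3 SD at r = 0.5 gives a non-centrality of 0.3 × √30 / 1.00 = 1.64 and is significant in 36% of trials. A shift of 0.5 SD at r = 0.7 gives 0.5 × √30 / 0.775 = 3.54 and is significant in 93%. The planned test cannot tell either from an effect of targeting.

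**6. Questionnaires.** Section 5 plans incontinence and quality-of-life questionnaires at 6 months. Appendix 1 marks neither at visit 4, and section 8.4 mentions only repeat MAPLe. If the schedule is followed, the questionnaire half of 11.2 has no post-treatment data.

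**The case against.** The best reply is that regression to the mean may be slight. Treatment is decided at the local MDT under current practice, and section 3 describes stepwise referral guided by response on FI scores. The Rationale also cites a lack of correlation between ARP and FI scores, so selection on symptoms need not be selection on physiology. Participants are symptomatic specialist referrals, and most may be treated. All of this stands. A reader might infer from the lower rows of the table that the plan carries a false-positive rate of 28–91%. The documents do not support that, because no section says treatment goes to those lowest on MAPLe, or that treatment groups will number 30.

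A reader might also infer that practice on the device alone would count as success. Under 11.2 it would not, since questionnaires must improve too. It could suffice under the MAPLe-only rule in section 5, the Summary and 11.5.2, and only if biofeedback was in fact delivered with MAPLe, which the protocol does not say for this study.

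Finally, it is tempting to say the study already holds usable comparators. Medication is a listed option ("The treatment options for FI include: medications, biofeedback, rectal irrigation, neuromodulation and other surgical interventions") with no group in 11.5.2, and some participants may not have started treatment by 6 months. But no section shows how many there would be, and they would differ by indication in ways that baseline adjustment does not remove. Even 30 against 30 would have only 21% power for 0.3 SD and 49% for 0.5 SD (two-sided 0.05). Nor are two other devices adequate repairs. Splitting the three squeezes within a session leaves between-visit variation untouched. A contrast of targeted with other sites has no evident target site for irrigation or neuromodulation.

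None of this rescues the inference from improvement to targeting.

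**Conclusion.** The concern holds as a fault in a stated rule: the plan draws a conclusion about targeting from an uncontrolled change that contains no information on targeting. That part rests on the text alone. The contribution of regression to the mean cannot be sized from the documents. It runs from none (about 2.5%, the nominal rate) to severe (59–91%), depending on how selection for treatment relates to baseline MAPLe, and it assumes reliability of 0.8 to 0.6 and 30 per treatment group. The point should be corrected because the secondary conclusion does not follow from its analysis. It does not affect the primary outcome.

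**What to change.** - In 11.2, section 5 and the Summary, replace the claim that targeted treatment was achieved with change in MAPLe and in St Mark's score from baseline to 6 months after treatment. Bring the secondary objective (section 4 and the Summary) and 11.5.2 into line.
- Report that change descriptively by treatment group, with confidence intervals. State that it does not show that treatment was targeted or that MAPLe assessment caused the change.
- Record on the CRF whether MAPLe was used to deliver biofeedback, and report those participants separately.
- Reconcile section 5 with Appendix 1 on the 6-month questionnaires, so that the questionnaire half of the outcome is collected.

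The cost is a more modest claim, one added CRF field and, if the schedule reflects current practice, a questionnaire at a visit already planned. A control arm or a comparison with untreated or medication-only participants is not required for this correction.
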